9.3.4 SAFETY ANALYSES

All safety data will be descriptively summarized by treatment groups and analyzed using the safety population.

Treatment Emergent Adverse Events (TEAE)s are defined as Aes that first occurred or worsened in severity after the initiation of online or in-person visits. The number of TEAEs as well as the number and percentage of patients who experienced at least 1 TEAE will be summarized using Medical Dictionary for Regulatory Activities for each system organ class (or a body system) and each preferred term by intervention group. SAEs and Aes that lead to discontinuation of the study intervention will also be summarized by the intervention group.

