4 STUDY DESIGN

4.1 OVERALL DESIGN

This study is testing the hypothesis that team-based connected health (TCH) model results in equivalent improvements in disease severity and quality of life, provides better access to specialist care, and is cost-saving as compared to usual in-person care for management of patients with atopic dermatitis (AD).

This is a 12-month, pragmatic, randomized, controlled, equivalency trial to evaluate the impact of an online, team-based connected health (TCH) model for management of atopic dermatitis (AD) as compared to in-person care. A total of 300 participants will be randomly assigned to the online TCH model or the in-person control arm.

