4.3 RATIONALE FOR INTERVENTION

Lack of access to dermatologic care and problems with traditional teledermatology models: In the U.S., access to dermatologists remains a significant challenge for many patients. Many patients have difficulties maintaining regular access to dermatologists due to factors such as lack of transportation or the inability to take time away from work for medical visits. Consequently, these patients with chronic skin diseases suffer from poor clinical outcomes and reduced quality of life.

Teledermatology is a specialty-care delivery model in which skin diseases are diagnosed and treated remotely by means of telecommunications technology.¹² While ample evidence supports accuracy and reliability of asynchronous teledermatology, few studies have examined patient outcomes. To develop more effective methods for specialty-care delivery, it is important to first recognize why traditional models of teledermatology have not worked well.¹³⁻²¹ Several key limitations exist with traditional consultative teledermatology. First, patients must find a nearby healthcare facility with telemedicine capabilities in order to access dermatologists online. Second, there is no direct contact between patients and the specialists, and this is the key reason for patient dissatisfaction. Third, the PCPs are variably effective in conveying and implementing specialists' recommendations.

Team-based connected health (TCH) model to provide expert care online. In this proposal, we will evaluate an online TCH model that provides high-quality, asynchronous online care for AD patients. Specifically, TCH will bring quality specialist care to patients and PCPs in a location-independent and asynchronous manner. Importantly, because dermatologists are central to the sustainability of this online model, the intervention is designed to maximally support the dermatologists.

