5.4 STRATEGIES FOR RECRUITMENT AND RETENTION

5.4.1 RECRUITMENT PLAN

In this pragmatic, randomized equivalency trial, we will recruit pediatric and adult patients with AD from both genders, diverse racial and ethnic groups, and across the full spectrum of AD severity. Patients will be randomized 1:1 stratified by age and study site to either the online TCH model or in-person visits for management of AD.²²

Medical records of patients with AD or eczema who had presented to the study sites since 2013 will be reviewed by the study staff to prescreen for eligibility. For patients who are potentially eligible, the study team will send these patients or their parents a letter that introduces the study. Following the letter, the study team will call these patients to inquire about their interest in the study.

In addition, the study team will also examine the clinic schedule and identify patients with visits for "eczema", "atopic dermatitis", "dermatitis", or other related terms. The study staff will contact these patients prior to their appointment to alert them that a study member may speak to them about the study on the day of their visit.

Other recruitment methods include flyers placed at the study sites, online and social media advertisements, ResearchMatch, local newspapers, and referral from colleagues. Selection is based solely on the participant's ability to meet the criteria stated in the protocol and his/her willingness to participate in the study.

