5.4.2 RETENTION PLAN

Prior to study initiation, we will conduct pre-trial retention training for the study staff. Prior to enrollment, the study staff will communicate with eligible patients regarding the importance of completing all outcome assessments. We will emphasize the importance of full participation during screening, enrollment, and throughout the trial.

It is important to note that, for online and in-person visits between the provider and patients, these visits occur at an individualized frequency based on medical necessity. However, the collection of outcome assessments (disease-severity, quality-of-life endpoints, and selected access-to-care measures) occurs at a quarterly basis for all participants.

All subjects will be reminded via email, text, or telephone to submit their quarterly outcome assessments beginning 7 days prior to the due date. If a subject fails to submit the quarterly outcome assessments within 2 days of the due date, the subject will be contacted using telephone and/or electronic methods to remind them to submit the assessments. The study staff will also discuss with the participant strategies to improve adherence with the study requirements. If the participant cannot be contacted after at least five attempts, a certified return receipt letter will be sent to encourage continuation in the trial.

If a participant fails to complete a quarterly assessment within 21 days of the due date, the study staff will make at least five attempts to contact (at least three telephone calls, two emails, and, if necessary, a certified return receipt letter to the participant's last known mailing address or local equivalent method). These contact attempts will be documented in the participant's study file.

If a participant wishes to withdraw from the study, the study coordinators will attempt to collect the Month 12 visit data as well as detailed data on the reasons for the discontinuation from the study. The study coordinators are encouraged to share their ideas and experiences to promote participant retention via regular communication during staff meetings.

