6.1.1.2 WHAT HAPPENS DURING AN ONLINE VISIT?

When the patient initiates an online visit, the platform begins a process with "required fields" to ensure completion of all required elements of an online visit before transmission to the dermatologist. Specifically, the patient uploads images of skin lesions and submits clinical history.

Within three business days, the dermatologist reviews the patient's history and images. The dermatologist then communicates the recommendations to the patient, prescribes the medications, and where appropriate, provides standard-care educational materials to patients online asynchronously.

The frequency of the follow-up online visits will be determined by the dermatologists and patients based on medical necessity.

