8.3.4 TIME PERIOD AND FREQUENCY FOR EVENT ASSESSMENT AND FOLLOW-UP

The occurrence of an adverse event (AE) or serious adverse event (SAE) may come to the attention of study personnel during study visits and interviews of a study participant presenting for medical care, or upon review by a study monitor.

All Aes including local and systemic reactions not meeting the criteria for SAEs will be captured on the appropriate case report form (CRF). Information to be collected includes event description, time of onset, clinician's assessment of severity, relationship to study product (assessed only by those with the training and authority to make a diagnosis), and time of resolution/stabilization of the event. All Aes occurring while on study must be documented appropriately regardless of relationship. All Aes will be followed to adequate resolution.

Any medical condition that is present at the time that the participant is screened will be considered as baseline and not reported as an AE. However, if the study participant's condition deteriorates at any time during the study, it will be recorded as an AE.

Changes in the severity of an AE will be documented to allow an assessment of the duration of the event at each level of severity to be performed. Aes characterized as intermittent require documentation of onset and duration of each episode.

The principal investigator or designated study staff member will record all reportable events with start dates occurring any time after informed consent is obtained until 7 (for non-serious Aes) or 30 days (for SAEs) after the last day of study participation. During each scheduled assessment, study subjects will be asked to complete a form to capture any occurrence of AE/SAEs since the last visit. Events will be followed for outcome information until resolution or stabilization.

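### Treatment-emergent adverse events are counted from an unscheduled post-randomisation date, the start of visits, which can differ by arm; counting from randomisation would give both arms the same starting point.

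*Combined protocol and SAP*

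**What the plan says.** Section 9.3.4 (Safety Analyses) defines TEAEs as "Aes that first occurred or worsened in severity after the initiation of online or in-person visits". It tabulates, by intervention group, the number of TEAEs and the number and percentage of patients with at least one, by system organ class and preferred term. No adjustment for length of exposure is described. SAEs, and AEs leading to discontinuation of the intervention, are summarised under a separate sentence that is not limited to TEAEs. The analysis set is called the safety population, but neither section 9.2 nor any other section defines it.

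Collection is wider than counting. Under section 8.3.4, staff "will record all reportable events with start dates occurring any time after informed consent is obtained until 7 (for non-serious Aes) or 30 days" (the longer limit applies to SAEs) after the last day of participation.

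The Schedule of Activities (section 1.3) places randomisation at Month 0 and assessments every quarter, but lists no first care visit. Section 5.4.2 says of online and in-person care that "these visits occur at an individualized frequency based on medical necessity".

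**The concern.** A safety comparison between randomised arms should observe both arms from the same point. Randomisation is that point. The first care visit comes later, at a time set by the patient, the provider and the route of access, and the route of access is what this trial randomises. Section 4.1 hypothesises that the online model "provides better access to specialist care, and is cost-saving as compared to usual in-person care". If the arms reach their first visits at different speeds, the arm that starts later has a shorter TEAE window, because the closing date does not move with the first visit. Equal true event rates would then show as unequal counts and percentages.

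Two further effects follow from reading the rule patient by patient. Events between randomisation and the first visit, including worsening dermatitis, fall outside the TEAE table although they are recorded. A patient who never has a visit has no TEAE period, and the undefined safety population leaves open whether that patient stays in the denominator.

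**Working it through.** The plan states no TEAE rate and no time to first visit, so there is no figure of its own to reproduce. The check sets the relevant rules side by side and then sizes the effect under stated assumptions.

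**The rules together**
- Counting starts at initiation of visits (section 9.3.4).
- That date is unscheduled in both arms (sections 1.3, 5.4.2 and 6.1.1.2).
- Recording starts at consent and closes 7 days (non-serious) or 30 days (serious) after the last day of participation (section 8.3.4).
- No section resets the TEAE start to randomisation.

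For a patient who completes follow-up, each day of delay to the first visit therefore removes one day from the TEAE window.

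**Illustration 1: a 52-week window.** Assumptions, none taken from the documents: a 40% 12-month risk of at least one AE in both arms, a constant event rate, and every patient in an arm having the same delay.
- Weekly rate = −ln(1 − 0.40)/52 = 0.00982.
- Counted risk with first visit at week w = 1 − exp(−rate × (52 − w)).

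| First visit | Counted risk | Gap from the week 1 arm |
|---|---|---|
| Week 1 | 39.4% | – |
| Week 4 | 37.6% | 1.8 points |
| Week 8 | 35.1% | 4.3 points |
| Week 12 | 32.5% | 6.9 points |

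With 300 patients randomised 1:1, or 150 per arm before attrition, the range is 150 × 0.018 = 2.7 to 150 × 0.069 = 10.4, so about 3 to 10 patients. Swapping the arms reverses the sign, and equal delays give a gap of zero. If only half of the slower arm waits until week 12 and the rest start at week 1, the gap halves to about 3.5 points.

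**Illustration 2: adding the 7-day tail for non-serious AEs.** Window = 365 + 7 − delay in days. P(at least one TEAE) = 1 − exp(−rate × window/365). The faster arm starts on day 0, so its window is 372 days. The rates are assumed.

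| Events per patient-year | No delay | 30-day delay (342 days) | Gap | 90-day delay (282 days) | Gap |
|---|---|---|---|---|---|
| 0.25 | 22.5% | 20.9% | 1.6 | 17.6% | 4.9 |
| 0.5 | 39.9% | 37.4% | 2.5 | 32.0% | 7.9 |
| 1 | 63.9% | 60.8% | 3.1 | 53.8% | 10.1 |
| 2 | 87.0% | 84.6% | 2.4 | 78.7% | 8.3 |

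Expected event counts in the delayed arm fall to 342/372 = 91.9% and 282/372 = 75.8% of the other arm's.

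**After the change.** Counting from randomisation gives completers in both arms the same 372-day window. At equal true rates the expected percentages are then equal, at the values in the no-delay column.

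**The case against.** A reader might infer that the table undercounts in-person events and shows a false excess with the online model. The documents do not support that direction.
- In section 6.1.1.2, "Within three business days, the dermatologist reviews" describes a response time that runs from the patient's submission. Nothing sets the time from randomisation to the first submission.
- Section 4.3 says "Many patients have difficulties maintaining regular access to dermatologists", but as general background, not as a measured wait at the study clinics.
- Better access is a hypothesis under test.
- Section 5.4.1 allows for patients with booked appointments that "a study member may speak to them about the study on the day of their visit", and section 5.1 admits patients with established care. Some in-person patients could be seen at or near enrolment, while an online patient might submit nothing for weeks. The difference could be nil or reversed.

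A reader might also infer that harm while waiting for care is lost from the trial. That goes too far. AEs are recorded from consent and go in aggregate to the DSMB (section 8.3.5), the SAE summary is not worded as TEAE-only, and EASI, vIGA and POEM are collected quarterly from all participants whatever their care visits. The safety analysis is descriptive, with no planned test.

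Finally, the wording could mean the start of the assigned care period rather than each patient's first visit, which would largely remove the problem.

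All of this limits the point. It does not settle the definition: the text does not say which reading applies, and two analysts could produce different TEAE tables from the same data.

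**Conclusion.** The point holds in conditional form. Read patient by patient, the TEAE start is an unscheduled post-randomisation date that can differ by arm. If it does differ, the by-arm counts and percentages are not comparable. Whether it differs, in which direction and by how much cannot be determined from the documents.

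The illustrative gap of about 2 to 7 percentage points rests on an assumed 40% risk, a constant and equal event rate, and a delay of 4 to 12 weeks against 1 week applied to every patient in the arm. Under the other assumptions tried, the gap is 1.6 to 3.1 points at a 30-day delay and 4.9 to 10.1 points at a 90-day delay. The sign follows whichever arm is delayed. The consequence is confined to one descriptive table and does not touch the primary endpoint. It is still worth correcting, because the change costs almost nothing and removes a foreseeable artefact.

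**What to change.** In section 9.3.4:
- Define TEAEs as AEs with onset or worsening on or after randomisation, through the end of AE collection in section 8.3.4.
- Define the safety population as all randomised patients, analysed by assigned arm, so that patients with no visit stay in the denominator.
- Show events with onset before the first care visit as a separate row in each arm.

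Exposure-adjusted rates would be a useful addition, since a common start equalises the windows only where follow-up is also equal.

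The cost is a few lines of analysis text. Section 8.3.4 already has staff "record all reportable events with start dates occurring any time after informed consent is obtained", so no new AE collection is needed. The separate row also needs the date of each patient's first care visit.

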9.3.5 BASELINE DESCRIPTIVE STATISTICS

Demographic and baseline characteristics will be summarized descriptively by treatment group. Descriptive statistics including number of patients, mean, standard deviation, median, minimum, and maximum will be provided for continuous measures, and frequency counts and percentages will be tabulated for categorical measures.

10 SUPPORTING DOCUMENTATION AND OPERATIONAL CONSIDERATIONS

10.1 REGULATORY, ETHICAL, AND STUDY OVERSIGHT CONSIDERATION

10.1.1 INFORMED CONSENT PROCESS

10.1.1.1 CONSENT/ASSENT AND OTHER INFORMATIONAL DOCUMENTS PROVIDED TO PARTICIPANTS

Electronic consent forms describing in detail the study intervention, study procedures, and risks are given to the participant and electronic documentation of informed consent is required prior to starting intervention/administering study intervention. The following electronic consent materials are submitted with this protocol: Adult Informed Consent Form and Youth Assent Form.

10.1.1.2 CONSENT PROCEDURES AND DOCUMENTATION

The informed consent is a process that is initiated prior to the individual's agreeing to participate in the study and continues throughout the individual's study participation. Consent forms will be Institutional Review Board (IRB)-approved and the participant will be asked to read and review the document.

Only the trained study staff listed on the protocol will obtain informed consent. Specifically, the study staff will explain the study procedures, benefits, and risks in detail to the interested adult patients. A verbal explanation will be provided in terms suited to the participant's comprehension of the purposes, procedures, and potential risks of the study and of their rights as research participants. Participants will have the opportunity to carefully review the electronic consent form through the NORA® platform and ask questions prior to providing an electronic signature. The participants should have the opportunity to discuss the study with their family or surrogates or think about it prior to agreeing to participate. The participant will sign the informed consent document electronically prior to any procedures being done specifically for the study. Participants must be informed that participation is voluntary and that they may withdraw from the study at any time, without prejudice. A copy of the electronically-signed informed consent document will be available to the participants to print for their records via an emailed link. The informed consent process will be conducted and documented in the electronic source document (including the date), and the form electronically signed, before the participant undergoes any study-specific procedures. The rights and welfare of the participants will be protected by emphasizing to them that the quality of their medical care will not be adversely affected if they decline to participate in this study.

We take special care with the assent process for minors and will adhere to all applicable institutional, state, and federal guidelines. Following the established USC IRB guidelines, we will review the study process with all minors below age 18 and his/her parent(s). For minors between 13-17 years of age and who agree to participate in the study, we will utilize the University of Southern California (USC) IRB-

approved Adult Informed Consent/Youth Assent/Parental Permission Form to be electronically signed by both the minor and the parents or legal guardian. If the minor is between the ages of 7 to 12 years of age, the study staff will review the IRB- approved "Assent to be in Research" with the minor (to be electronically signed by the minor), and his or her parents or legal guardian will electronically sign the Adult Informed Consent/Youth Assent/Parental Permission Form. If the minor is between ages 4 to 6, the study staff will speak with the minor in age-appropriate language to explain the details of the study. This discussion will occur in the presence of the parent(s) and one other staff member serving as a witness. The study staff will thoroughly document the details of the discussion. If the minor expresses any hesitation to participating in the study, the minor will not be enrolled in the study. If the minor expresses willingness to participate in the study, his or her parents or legal guardian(s) will electronically sign the Adult Informed Consent/Youth Assent/Parental Permission Form. For minors between ages 1 to 3, the study staff will obtain parental permission using a USC IRB-approved the Adult Informed Consent/Youth Assent/Parental Permission Form. In all cases, both parents must give their permission via electronic signature unless one parent is deceased, unknown, incompetent, or not reasonably available, or when only one parent has legal responsibility for the care and custody of the child.

10.1.2 STUDY DISCONTINUATION AND CLOSURE

This study may be temporarily suspended or prematurely terminated if there is sufficient reasonable cause. Written notification, documenting the reason for study suspension or termination, will be provided by the suspending or terminating party to study participants, investigators, funding agency, and regulatory authorities. If the study is prematurely terminated or suspended, the Principal Investigator (PI) will promptly inform study participants, the Institutional Review Board (IRB), and sponsor and will provide the reason(s) for the termination or suspension. Study participants will be contacted, as applicable, and be informed of changes to study visit schedule.

Circumstances that may warrant termination or suspension include, but are not limited to:

- Determination of unexpected, significant, or unacceptable risk to participants
- Demonstration of efficacy that would warrant stopping
- Determination that the primary endpoint has been met

Study may resume once concerns about safety, protocol compliance, and data quality are addressed, and satisfy the sponsor and IRB.

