9 STATISTICAL CONSIDERATIONS

9.1 SAMPLE SIZE DETERMINATION

We consider $\delta_U = \pm 6.5$ as the equivalence limit for our primary outcome, SA-EASI, which is half of a clinically significant difference and much more conservative than prior studies.¹¹ We computed sample size estimates for equivalency comparison of means for the primary endpoint and secondary endpoints from Aim 1 and Aim 2 using one-sided $\alpha = 0.05$ and 80% power (PASS version 14). 272 patients randomized are sufficient to determine equivalency with 80% power for the primary endpoint of EASI given the range of SD (15-20), with anticipated 15% attrition. This N is larger than that required for any

of the other outcomes.²³⁻²⁵ Thus, enrolling 300 patients provides adequate power to evaluate primary and all secondary outcomes and accounts for attrition.

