9.3.2 ANALYSIS OF THE PRIMARY EFFICAY ENDPOINTS

The primary endpoint of the study is the mean improvement from baseline in EASI versus the follow-up visits (months 3-12). The comparison of improvement in EASI will incorporate all available post-intervention follow-up visits. Our primary goal will be to compare the mean difference in improvement between groups to examine if they are equivalent.

We will use an intent-to-treat (ITT) approach to evaluate equivalency of changes between the two arms across 12 months for AD-disease-severity and quality-of-life endpoints using longitudinal linear mixed modeling. This modeling allows us to account for intra-individual variability and the possibility of different numbers of follow-up measurements inherent in this pragmatic research design. For these analyses, the null hypothesis is that there is a differential treatment effect between the groups: H_0 : $\mu I_{n-person} \neq \mu_{TCH}$. The alternate hypothesis is H_A : $\mu_{In-person} = \mu_{TCH}$, where μ represents the average change from baseline across the follow-up visits (3 months – 12 months).

For the primary comparison of baseline versus average of follow-up visits, a dummy-coded time variable will be coded with 0 = baseline and 1 for all follow-up visits, so that the estimate of the effect will indicate the difference between baseline and the average of follow-up visits. In addition, a group

variable will be added to the model (coded 0 for in-person and 1 for TCH) along with a group x time effect.

We consider $\delta_0 = \pm 6.5$ as the equivalence limit for the primary endpoint of EASI. This equivalence limit of 6.5 was selected for EASI because it represents the minimal clinically important difference in the AD literature.²⁸ It is also more conservative than equivalency limits of 12-20 from pilot studies.²⁹

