10.1.4 SAFETY OVERSIGHT

Safety oversight will be under the direction of a Data and Safety Monitoring Board (DSMB) composed of individuals with the appropriate expertise, including dermatology, teledermatology, and inflammatory skin diseases. Members of the DSMB should be independent from the study conduct and free of conflict of interest, or measures should be in place to minimize perceived conflict of interest. The DSMB will meet semi-annually to assess safety and efficacy data on each arm of the study. The DMSB will operate under the rules of an approved charter that will be written and reviewed at the organizational meeting of the DSMB. The DSMB will provide its input to the National Institute of Arthritis and Musculoskeletal and Skin Diseases.

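### Section 10.1.2 allows the trial to end on efficacy or a met primary endpoint, but the protocol and SAP set no interim boundary, so acting on those grounds could push the false-equivalence rate above 5%

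*Combined protocol and SAP*

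**What the plan says.** Section 10.1.2 (Study Discontinuation and Closure) gives an open-ended list of reasons that could justify suspending or ending the trial. Two of them concern efficacy: "Demonstration of efficacy that would warrant stopping" and "Determination that the primary endpoint has been met". Neither has a numerical criterion or a named decision-maker.

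Section 10.1.4 (Safety Oversight) states: "The DSMB will meet semi-annually to assess safety and efficacy data on each arm of the study". On the rules the board will follow, it says: "The DMSB will operate under the rules of an approved charter that will be written and reviewed at the organizational meeting of the DSMB". The charter is not among the documents, and section 10.1.4 does not mention a statistical boundary.

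Section 9.1 bases the sample size on a one-sided alpha of 0.05 and 80% power, and concludes: "272 patients randomized are sufficient to determine equivalency with 80% power for the primary endpoint of EASI". It takes the SD to lie between 15 and 20 and allows for 15% of patients dropping out. Planned enrolment is 300. Section 9.3.2 takes ±6.5 "as the equivalence limit for the primary endpoint of EASI" and describes one comparison over months 3-12. Nowhere does section 9 describe an interim analysis, a number of looks, a boundary, alpha spending or an adjusted final critical value.

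**The concern.** The protocol provides occasions on which efficacy is seen by arm and grounds on which efficacy could end the trial. The statistical section is written as if there will be one test at full alpha. If a favourable look could close the trial with equivalence declared, there would be several chances to succeed, each at 0.05, and the overall risk of wrongly declaring TCH equivalent to in-person care would exceed 5%.

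There is a second, lesser risk. The endpoint averages follow-up from month 3 to month 12 and uses whatever visits are available. Closing the trial early could leave enrolled patients with only their earlier visits, weakening a 12-month claim, unless they are allowed to complete follow-up.

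**Working it through.** **Inputs from the documents.** Margin ±6.5 (9.1, 9.3.2); one-sided alpha 0.05 (9.1); SD 15-20 and 15% attrition (9.1); 300 patients (9.1), randomized 1:1 (5.4.1); study duration 60 months and participant duration 12 months (1.1).

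**Assumptions, not in the documents.** The number of looks; equal spacing of information; equivalence declared at the first look where the 90% confidence interval lies wholly inside ±6.5.

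**Plan's own figure.** Per arm, n = 2(z₀.₉₅ + z₀.₈₀)²SD²/6.5². With SD 20 this is 2 × (1.645 + 0.842)² × 400/42.25 ≈ 117.1, so 118 per arm and 236 in total; 236 × 1.15 = 271.4, so 272. The stated figure thus reproduces with the whole 0.05 given to one analysis. (The two-sided equivalence formula, with z₀.₉₀ in place of z₀.₈₀, gives 236 only at SD 17. That is a separate matter.)

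**Precision at the final look.** Evaluable per arm = 300 × 0.85/2 = 127.5. SE = SD × √(2/127.5), which is 1.88 at SD 15 and 2.50 at SD 20.

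**When success first becomes possible.** At information fraction t the interval fits inside ±6.5 only if 1.645 × SE/√t < 6.5, so t > (1.645 × SE/6.5)². This is 0.23 at SD 15 and 0.40 at SD 20. Earlier looks cannot declare equivalence, so they add nothing to the error.

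**Two looks at SD 20, true difference 6.5.** At half information SE = 2.50 × √2 = 3.54. Success needs an estimate within ±(6.5 − 1.645 × 3.54) = ±0.67. Its probability is Φ(−1.645) − Φ(−2.02) = 0.050 − 0.021 = 2.9%. Simulation adds 4.1% for trials that first succeed at the final look, giving 7.0%. At SD 15 the parts are 4.9% and 3.1%, giving 8.0%.

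**False-equivalence rate at a true difference of 6.5** (1,000,000 simulated trials per setting; looks include the final analysis):

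| Looks | SD 15 | SD 20 |
|---|---|---|
| 1 | 5.0% | 5.0% |
| 2 | 8.0% | 7.0% |
| 4 | 10.1% | 8.6% |
| 8 | 12.6% | 10.0% |

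**Which look counts are plausible.** With only completers counted, recruitment over 48 months leaves (60 − 12)/6 = 8 semi-annual looks. Recruitment over 24 months gives 24/6 = 4. The documents state no recruitment period.

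**With O'Brien-Fleming-type (Lan-DeMets) spending on each one-sided test.** The final critical value becomes about 1.665, 1.724 and 1.782 for 2, 4 and 8 looks, and false equivalence is 4.6-4.9%. At N = 300 with 15% attrition and no true difference, power falls from 93.0% to 92.8%, 92.2% and 91.8% at SD 15, and from 65.8% to 64.8%, 63.3% and 61.9% at SD 20.

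**The case against.** The strongest reply is that section 10.1.2 is general closure language. It is permissive, gives no test, and its sentence on resuming the study mentions only safety, compliance and data quality. The DSMB review sits under safety oversight, the board gives input to NIAMS, and nothing ties its meetings to the two efficacy grounds. Boundaries may properly be placed in a charter.

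Much of this stands, and it rules out several stronger readings that a reader might infer:

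- *The DSMB formally tests equivalence every six months.* The documents neither say this nor exclude it. Looking at efficacy data costs no alpha unless a look can lead to stopping with success declared.
- *No boundary exists at all.* The documents support only that none appears in the protocol or SAP; the charter is unseen.
- *A met endpoint is defined as an interval inside ±6.5.* Section 9.3.2 gives a margin and point hypotheses but no interval or two-one-sided-tests rule, so that reading is an assumption.
- *A 60-month study means ten informative looks.* With 12 months of follow-up per patient, the early meetings would hold little or no endpoint information.
- *Early stopping must cut off follow-up.* Section 10.1.2 does not say whether enrolled patients would finish.

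The reply does not remove the point. The protocol names a met primary endpoint as a reason to end the trial, and section 9 has no means of using that reason while holding the error at 5%. If the charter does hold a boundary, its effect on the final critical value would still need to appear in section 9.

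**Conclusion.** The point holds conditionally. As written, the protocol and SAP do not protect the one-sided 0.05 if either efficacy ground in section 10.1.2 is acted on. The excess is roughly 2 to 8 percentage points across two to eight assumed looks. It is evaluated at a true difference exactly on the margin, where the error is greatest. It would be zero if no look can stop the trial for equivalence, and close to zero if the charter applies a proper boundary that is carried to the final analysis. This is a defect of wording that would give a wrong error rate if used; it is not evidence that the trial will be stopped in this way.

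**What to change.** Delete the two efficacy grounds from section 10.1.2. State in sections 9 and 10.1.4 that DSMB reviews cannot stop the trial for equivalence, and that the single equivalence test is done after the last 12-month visit. The board need not lose sight of efficacy: by-arm severity data can stay in its reports for safety, since section 2.2.3 names worsening of AD as a risk in both arms. This keeps the rate at 5.0% with no loss of power. The cost is a wording amendment and the loss of the option to stop early for equivalence.

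If that option is wanted, section 9 should define when the endpoint counts as met, give the number and timing of looks, apply O'Brien-Fleming-type spending to both one-sided tests, and use the adjusted critical value at the final analysis. It should also say whether enrolled patients complete month 12 after a stop. The power cost is about 0.2 to 1.2 percentage points at SD 15 and 1 to 4 points at SD 20 for two to eight looks. The charter should match.
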